4.2.2.2 Atezolizumab

Cohort A: Patients will initiate dosing with atezolizumab concurrently with cobimetinib and will receive atezolizumab 840 mg IV Q2W on Days 1 and 15 of all cycles.

Cohort B: Patients will receive the first dose of atezolizumab at 840 mg IV on Day 15 of Cycle 1. Thereafter, they will receive atezolizumab 840 mg IV Q2W on Days 1 and 15 of Cycle 2 and all subsequent cycles.

Cohort C: Patients will receive atezolizumab 1200 mg IV Q3W as monotherapy.

All dosing schedules will be given in a monitored setting where there is immediate access to trained personnel and adequate equipment/medicine to manage potentially serious reactions.

For more detailed information on drug preparation, storage, and administration, refer to the Atezolizumab Investigator's Brochure and Pharmacy Manual.

Atezolizumab infusions will be given per the instructions outlined in [Table 2](#).

Table 2 Administration of First and Subsequent Infusions of Atezolizumab

First Infusion	Subsequent Infusions
Premedication is allowed.	If patient experienced IRR during any previous infusion, premedication with antihistamines may be administered for Cycles ≥ 2 at the discretion of the treating physician.
Record vital signs (HR, RR, BP, and T) within 60 minutes before starting infusion.	Record vital signs (HR, RR, BP, and T) within 60 minutes before starting infusion.
Infuse atezolizumab (one vial in 250 mL NaCl) over 60 (± 15) minutes	If the patient tolerated the first infusion without infusion-associated AEs, the second infusion may be delivered over 30 (± 10) minutes.
Record vital signs (HR, RR, BP, and T) during the infusion or after the infusion if clinically indicated	If the patient had an IRR during the previous infusion, the subsequent infusion must be delivered over 60 (± 15) minutes. Record patient's vital signs (HR, RR, BP, and T) during the infusion or after the infusion if clinically indicated or patient experienced symptoms during the previous infusion.
Patients will be informed about the possibility of delayed post-infusion symptoms and instructed to contact their study physician if they develop such symptoms.	If no reaction occurs, continue subsequent infusions over 30 (± 10) minutes with same schedule for recording vital signs.

AE = adverse event; BP = blood pressure; HR = heart rate; IRR = infusion-related reaction; NaCl = sodium chloride; RR = respiratory rate; T = temperature.

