5.1.3.3 Management of Cobimetinib- and Atezolizumab-Specific Adverse Events

Toxicities associated or possibly associated with cobimetinib plus atezolizumab treatment should be managed according to standard medical practice. See [Appendix 8](#) for management of adverse events related to atezolizumab.

For management of cobimetinib- and atezolizumab-specific toxicities, including IRRs, gastrointestinal toxicity, dermatologic toxicity, hepatotoxicity, pulmonary toxicity, potential eye toxicity, reductions in LVEF from baseline, rhabdomyolysis, elevated CPK, and hemorrhage, see [Table 6](#).

Table 6 Guidelines for Management of Patients Who Experience Specific Adverse Events (Cobimetinib and Atezolizumab)

Event	Action to Be Taken

General guidance for dose modifications and treatment delays and discontinuation
	
 • There will be no dose modifications for atezolizumab. • If atezolizumab is withheld and corticosteroids are initiated for an atezolizumab-related toxicity, corticosteroids must be tapered over ≥ 1 month to ≤ 10 mg/day oral prednisone or equivalent before atezolizumab can be resumed.^{a, b, c} 
The dose of cobimetinib can be reduced by 20 mg (one dose level) up to two times (i.e., from 60 mg to 40 mg and then from 40 mg to 20 mg). If further dose reduction is indicated after two dose reductions, the patient must discontinue cobimetinib but may continue treatment with atezolizumab at the investigator's discretion.
 
 • If atezolizumab is discontinued, treatment with cobimetinib may be continued at the investigator's discretion and after discussion with the Medical Monitor. • If cobimetinib is withheld for > 28 days because of toxicity, the patient should be discontinued from cobimetinib, unless resumption of treatment is approved by the Medical Monitor after discussion with the investigator. • If atezolizumab is withheld for > 105 days because of toxicity, the patient should be discontinued from atezolizumab, unless resumption of treatment is approved by the Medical Monitor after discussion with the investigator.

IRRs, anaphylaxis, and hypersensitivity reaction
	
 • Guidelines for management of IRRs are provided in Appendix 8. • For anaphylaxis precautions, see Appendix 7. • For severe hypersensitivity reactions, permanently discontinue all study treatment.

IRR=infusion-related reaction.

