- ^u In Cohort A, atezolizumab will be given on Days 1 and 15 of all cycles. The initial dose will be delivered over 60 (\pm 15) minutes. If the first infusion is well tolerated, all subsequent infusions will be delivered over 30 (\pm 10) minutes until loss of clinical benefit. Study drug administration may be \pm 3 days from the scheduled Day 1 and 15 of each cycle.
- ^v Cobimetinib 60 mg/day by mouth will be given in a 21/7 dosing schedule.

Appendix 1
Schedule of Activities (cont.)
Cohort B: Biopsy Cohort

	Screening ^a	Cycle 1		Cycle 2		Cycle 3+		Treatment Discontinuation ^b	Unplanned Visit ^c	Survival FU ^d
Day (window)	-35 to -1	1	15	1	15	1	15	30 (±3) days after last dose		Q3M
Informed consent ^e	x									
Demographic data	x									
Medical history	x									
Vital signs ^{f,g}	x	x	x	x	x	x	x	x	x	
ECOG PS	x	x		x		x			x	
Weight	x	x		x		x		x		
Height	x									
Complete physical examination	x							x		
Limited physical examination		x ^h		x		x				
Hematology ⁱ	x	x		x		x		x	x	
Coagulation (INR and aPTT)	x									
BRAF ^{V600} WT mutation status	x									
PK and ADA sample for atezolizumab	See Appendix 2								x	x
PK sample for cobimetinib	See Appendix 2									
Serum samples for auto-antibody tests ^j		x								

Appendix 1
Schedule of Activities (cont.)
Cohort B: Biopsy Cohort

	Screening ^a	Cycle 1		Cycle 2		Cycle 3+		Treatment Discontinuation ^b	Unplanned Visit ^c	Survival FU ^d
Day (window)	-35 to -1	1	15	1	15	1	15	<30 (±3) days after last dose		Q3M
Optional WGS		x								
Chemistry ^k	x	x		x		x		x	x	
Tumor assessments ^l	x	Scans will be done every 8 weeks ± 7 days								
ECHO/MUGA scan	x			x		x ^m		x	x	
ECG (average of triplicate measurements)	x								x	
Serology ⁿ	x									
Thyroid function ^o	x	x		x		x ^o		x		
Ophthalmologic exam	x	Perform ophthalmology investigations as per Section 4.4.7.								
Pregnancy test ^p	x	x		x		x ^p		x	x	
Urinalysis ^q	x									
Concomitant medications ^r	x ^r	x ^r		x		x		x ^r		
Adverse events ^s	x ^s	x ^s	x	x	x	x	x	x ^s		x ^s
Tumor biopsy ^t	x		x ^u	x				x		
Biomarker blood samples		See Appendix 2								
Atezolizumab administration ^v			x	x	x	x	x			
Dispense cobimetinib ^w		x		x		x				
Survival and anti-cancer therapy FU										x

Appendix 1

Schedule of Activities (cont.)

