A subsequent mandatory biopsy will be performed between Days 10 and 14 of Cycle 1. An additional optional biopsy may be collected during Cycle 2, approximately 4–6 weeks after the first atezolizumab administration. A mandatory biopsy will be collected at the time of radiographic progression, if clinically feasible.
- ^u Days 10–14.
- ^v In Cohort B, atezolizumab will be given on Cycle 1, Day 15 and on Days 1 and 15 of all subsequent cycles. The initial dose will be delivered over 60 (\pm 15) minutes. If the first infusion is well tolerated all subsequent infusions will be delivered over 30 (\pm 10) minutes until a loss of clinical benefit. Study drug administration may be \pm 3 days from the scheduled Day 1 and 15 of each cycle.
- ^w Cobimetinib 60 mg/day by mouth will be given in a 21/7 dosing schedule. Dosing will start on Cycle 1, Day 1, 14 days before the first atezolizumab administration.

Appendix 1
Schedule of Activities (cont.)
Cohort C: Atezolizumab Monotherapy (21-Day Cycle)

Day (window)	Screening ^a	Cycle 1	Cycle 2	Cycle 3+	Treatment Discontinuation ^b	Unplanned Visit ^c	Survival FU ^d
	-35 to -1	1	1	1	30 (± 3) d after last dose		Q3M
Informed consent ^e	x						
Demographic data	x						
Medical history	x						
Vital signs ^{f, g}	x	x	x	x	x	x	
ECOG PS	x	x	x	x		x	
Weight	x	x	x	x	x		
Height	x						
Complete physical examination	x				x		
Limited physical examination		x ^h	x	x			
Hematology ⁱ	x	x	x	x	x	x	
Coagulation (INR and aPTT)	x						
BRAF ^{V600} WT mutation status	x						
PK/ADA sample for atezolizumab	See Appendix 2						
Serum samples for auto antibody tests ^j		x					
Optional WGS		x					

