No premedication is indicated for the administration of Cycle 1 of atezolizumab. However, patients who experience an infusion-related reaction (IRR) with Cycle 1 of atezolizumab may receive premedication with antihistamines or antipyretics/analgesics (e.g., acetaminophen) for subsequent infusions. Metamizole (dipyrone) is prohibited in treating atezolizumab-associated IRRs because of its potential for causing agranulocytosis.

Guidelines for medical management of IRRs during Cycle 1 are provided in [Table 7](#). For subsequent cycles, IRRs should be managed according to institutional guidelines.

Appendix 8

Risks Associated with Atezolizumab and Guidelines for Management of Adverse Events Associated with Atezolizumab (cont.)

Table 7 Management Guidelines for Infusion-Related Reactions

Event	Management
IRR, Grade 1	
 • Reduce infusion rate to half the rate being given at the time of event onset. • After the event has resolved, the investigator should wait for 30 minutes while delivering the infusion at the reduced rate. • If the infusion is tolerated at the reduced rate for 30 minutes after symptoms have resolved, the infusion rate may be increased to the original rate.
IRR, Grade 2	
 • Interrupt atezolizumab infusion. • Administer aggressive symptomatic treatment (e.g., oral or IV antihistamine, anti-pyretic medication, glucocorticoids, epinephrine, bronchodilators, oxygen). • After symptoms have resolved to baseline, resume infusion at half the rate being given at the time of event onset. • For subsequent infusions, consider administration of oral premedication with antihistamines, anti-pyretics, and/or analgesics and monitor closely for IRRs.
IRR, Grade 3 or 4	
 • Stop infusion. • Administer aggressive symptomatic treatment (e.g., oral or IV antihistamine, anti-pyretic, glucocorticoids, epinephrine, bronchodilators, oxygen). • Permanently discontinue atezolizumab and contact Medical Monitor.^a

IRR=infusion-related reaction.

^a Resumption of atezolizumab may be considered in patients who are deriving benefit and have fully recovered from the immune-related event. Patients can be re-challenged with atezolizumab only after approval has been documented by both the investigator (or an appropriate delegate) and the Medical Monitor.

Appendix 8

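### The Appendix 1 dosing footnotes set 30 minutes for every atezolizumab infusion after a tolerated first one, against Table 2's mandatory 60 minutes after an infusion-related reaction

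*Combined protocol and SAP*

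**What the plan says.** Section 4.2.2.2 (Atezolizumab) states "Atezolizumab infusions will be given per the instructions outlined in" Table 2. Table 2 then sets three rules for infusions after the first:

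- After a tolerated first infusion: "If the patient tolerated the first infusion without infusion-associated AEs, the second infusion may be delivered over 30" (±10) minutes. This is a permission.
- After an infusion with a reaction: "If the patient had an IRR during the previous infusion, the subsequent infusion must be delivered over 60" (±15) minutes. This is mandatory, and the trigger is the previous infusion, whichever number that was.
- The 30 (±10) minute duration then continues on condition that no reaction occurs.

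Appendix 1 restates the duration in three footnotes. Cohort A footnote u says "If the first infusion is well tolerated, all subsequent infusions will be delivered over 30" (±10) minutes until clinical benefit is lost. Cohort B footnote v says "If the first infusion is well tolerated all subsequent infusions will be delivered over 30" (±10) minutes, and Cohort C footnote u matches Cohort A. None of the three mentions IRRs or refers to Table 2.

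**The concern.** The footnotes make duration depend only on how the first infusion went. Table 2 makes it depend on the most recent infusion. The two part company when a patient tolerates the first infusion and reacts at a later one: Table 2 then slows the next infusion, while the footnotes keep it fast.

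The schedule is a working document for sites. Section 4.4 sends them to Appendix 1 for the activities to be performed, and the footnotes are worded as directions with numeric windows. Footnote g of the same schedule does carry a prior-reaction condition for taking vital signs during the infusion. A reader could reasonably infer that duration has no such condition. At stake is an infusion given faster than the protocol's own safety rule allows, to a patient who has just reacted. With approximately 60 centers (Section 9.4), different sites could follow different texts.

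**Working it through.** **Inputs.** Footnote duration 30 (±10) minutes (Appendix 1, Cohort A u, Cohort B v, Cohort C u). Table 2 duration after an IRR 60 (±15) minutes (Section 4.2.2.2). Dosing days from Section 4.2.2.2, with cycle lengths of 28 days (Cohorts A and B) and 21 days (Cohort C) from Section 3.1. The plan states no figure to reproduce on this point.

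**Can both texts be met?**

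- Footnotes: 30 − 10 = 20 to 30 + 10 = 40 minutes.
- Table 2 after an IRR: 60 − 15 = 45 to 60 + 15 = 75 minutes.
- Gap: 45 − 40 = 5 minutes. The windows do not overlap.

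**Size of the difference in rate.** The dose is the same under either text, so the rate ratio (footnote over Table 2) is the inverse ratio of durations.

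| Comparison | Ratio |
|---|---|
| Nominal durations | 60/30 = 2 |
| Slowest footnote infusion against fastest Table 2 infusion | 45/40 = 1.125 |
| Fastest footnote infusion against fastest Table 2 infusion | 45/20 = 2.25 |
| Fastest footnote infusion against slowest Table 2 infusion | 75/20 = 3.75 |

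At nominal durations this is 840/30 = 28 mg/min instead of 840/60 = 14 mg/min in Cohorts A and B, and 1200/30 = 40 mg/min instead of 1200/60 = 20 mg/min in Cohort C.

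**When it can first happen.** Infusion 1 must be tolerated for the footnote to apply. The earliest triggering IRR is therefore at infusion 2, and the earliest conflict at infusion 3. Weeks are counted from Cycle 1 Day 1.

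| Cohort | Infusion 1 | Infusion 2 | Infusion 3 |
|---|---|---|---|
| A | C1D1, week 0 | C1D15, week 2 | C2D1, week 4 |
| B | C1D15, week 2 | C2D1, week 4 | C2D15, week 6 |
| C | C1D1, week 0 | C2D1, week 3 | C3D1, week 6 |

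**How many infusions per reaction.** Table 2's requirement attaches to the infusion after the one with the IRR. Each IRR at infusion 2 or later, with treatment continued, therefore puts one infusion in direct conflict. A further IRR starts the count again.

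**Does any other text reconcile the two?**

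- Section 4.4.4 refers patients with a prior IRR to Section 5.3.5.1, which covers only how the reaction is recorded.
- Appendix 8 states "Guidelines for medical management of IRRs during Cycle 1 are provided in" its Table 7, and then "For subsequent cycles, IRRs should be managed according to institutional guidelines". Of the infusions at which a triggering IRR can occur (infusion 2 onward), Cycle 1 contains one in Cohort A (Day 15) and none in Cohorts B and C. Table 7's discontinuation rule for Grade 3 or 4 is therefore written for almost none of the relevant reactions, and it cannot be used to limit the conflict to Grades 1 and 2.
- Table 6 in Section 5.1.3.3 says "For severe hypersensitivity reactions, permanently discontinue all study treatment", but it refers the management of IRRs to Appendix 8.

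None of these gives an infusion duration that resolves the difference.

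**The second difference.** For infusion 2 after a tolerated first, Table 2 permits 30 minutes and the footnotes direct it. A 30-minute infusion complies with both, so this is a mismatch of wording only.

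**The case against.** The strongest reply is that Table 2 controls. Section 4.2.2.2 says so, Table 2's wording is mandatory, and a specific rule for an exceptional case ordinarily prevails over general shorthand in a visit schedule. On that reading the footnotes describe the normal course, and the matter is a minor editorial correction. It is true that Table 2 governs and that no rule is missing. But the footnotes cover all later infusions without qualification, so a site that relies on them is misdirected.

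Safeguards also exist. Infusions take place in a monitored setting and antihistamine premedication is allowed after an IRR (Section 4.2.2.2 and Table 2). Toxicity is assessed before each dose (Section 4.4). Vital signs are taken during the infusion if symptoms occurred at the prior one, and 30 (±10) minutes after every infusion (Appendix 1, footnote g). These lower the risk or help detect a reaction; none corrects the rate. Sites are also referred to a Pharmacy Manual that is not among the documents and may give the right duration.

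The 3.75 ratio is fairly criticised as pairing the two extremes. Table 2 accepts 45 minutes, so the excess over the fastest compliant rate is 1.125 to 2.25. Table 2 also does not say outright when a patient slowed to 60 minutes returns to 30. That ambiguity does not affect the count above, which rests only on the mandatory infusion.

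**Conclusion.** The concern holds. Three footnotes restate a safety instruction incorrectly, and at the infusion after an IRR they cannot be followed together with Table 2. The nominal rate is doubled at one infusion per reaction, from infusion 3 onward. This requires a tolerated first infusion, an IRR at a later one, and continued atezolizumab. How often that happens cannot be derived from the documents, and it may be rare. No efficacy analysis is affected. The correction should be made because the error concerns dosing after a reaction; it does not call the design into question.

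**What to change.** In Appendix 1, Cohort A footnote u, Cohort B footnote v and Cohort C footnote u, replace the duration text with: infusion duration per Table 2. Leave Table 2 unchanged. This is better than adding an IRR exception to each footnote, which would leave the permissive and directive wordings for the second infusion at odds and keep the rule in four places. The cost is a one-line edit to three footnotes at the next amendment, with no new procedures.

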Appendix 1 Schedule of Activities (cont.)

- ^h Perform a limited, symptom-directed examination at specified timepoints or as clinically indicated. Record new or worsened clinically significant abnormalities on the Adverse Event eCRF. If physical examinations are assessed within 7 days of the Cycle 1, Day 1 visit, they do not have to be repeated at Day 1.
- ⁱ Hematology includes WBC count, RBC count, hemoglobin, hematocrit, platelet count, reticulocyte count, differential count (neutrophils, eosinophils, basophils, monocytes, and lymphocytes).
- ^j Includes: anti-nuclear antibody, anti-double-stranded DNA, circulating anti-neutrophil cytoplasmic antibody, perinuclear anti-neutrophil cytoplasmic antibody.
- ^k Chemistry panel (serum or plasma) includes sodium, potassium, chloride, bicarbonate (or total carbon dioxide), BUN or urea, creatinine, total protein, magnesium, phosphorus, calcium, total and direct bilirubin, ALP, ALT, AST, CPK, LDH, uric acid; albumin, non-fasting glucose (fasting blood glucose after a minimum 8-hour fast, at screening only), and lipids (fasting lipids: total cholesterol, LDL cholesterol, and triglycerides after a minimum 8-hour fast, at screening only).
- ^l Tumor assessments will continue until disease progression per RECIST v1.1, loss of clinical benefit (patients who continue treatment after disease progression according to RECIST v1.1), consent withdrawal, study termination by the Sponsor, or death, whichever occurs first. At the investigator's discretion, tumor assessments may be repeated at any time if disease progression is suspected. Patients who discontinue treatment for reasons other than disease progression (e.g., toxicity) will continue scheduled tumor assessments until disease progression, withdrawal of consent, study termination by Sponsor, or death, whichever occurs first.
- ^m All patients will undergo evaluation of left ventricular dysfunction, either by ECHO or MUGA scan, at screening. Evaluation of LVEF by ECHO or MUGA scan must be performed at the following time points only for patients receiving cobimetinib:
- Cycle 2, Day 1 \pm 1 week
 - Day 1 of Cycles 5, 8, 11, 14, 17, etc. (every three treatment cycles; \pm 2 weeks)
 - Treatment discontinuation visit evaluation of LVEF does not need to be performed at treatment discontinuation visit if an evaluation has been performed within the last 12 weeks and there are no clinically significant findings and/or changes from baseline.
 - All patients restarting treatment with a dose reduction of cobimetinib because of a decrease in LVEF should have LVEF measurements taken after approximately 2, 4, 10, and 16 weeks, and then resume monitoring LVEF every three treatment cycles.
- ⁿ All patients will be tested for HIV prior to the inclusion into the study and HIV-positive patients will be excluded from the clinical study.
- HBV serology will include HBsAg, total HBcAg antibody (anti-HBcAb). HBV DNA should be obtained before study start if patient has a negative serology for HBsAg and a positive serology for anti-HBcAb.
 - HCV serology will include HCV antibody (anti-HCV). HCV RNA should be obtained prior to study start if patient tests positive for anti-HCV.

Appendix 1 Schedule of Activities (cont.)

- ^o Thyroid function testing (TSH, free T3 [or total T3 for sites where free T3 is not performed], free T4) collected at Day 1 of Cycles 1–5, and every second cycle thereafter (e.g., Day 1 of Cycles 7, 9, 11, etc.) for patients on atezolizumab only.
- ^p All women of childbearing potential will have a serum pregnancy test at screening within 14 days before Day 1 of Cycle 1. Urine pregnancy tests will be performed on Day 1 of every cycle and at the treatment discontinuation visit. If a urine pregnancy test is positive, it must be confirmed by a serum pregnancy test.
- ^q Includes dipstick (pH, specific gravity, glucose, protein, ketones, blood) and microscopic examination (sediment, RBCs, WBCs, casts, crystals, epithelial cells, bacteria).
- ^r Includes any medication (e.g., prescription drugs, over-the-counter drugs, herbal or homeopathic remedies, nutritional supplements) used by a patient from 7 days before initiation of study drug until 30 days after the last dose of study drug.
- ^s After informed consent has been obtained but before initiation of study drug, only serious adverse events caused by a protocol-mandated intervention should be reported. After initiation of study drug, all adverse events will be reported until 90 days after the last dose of study drug or initiation of new anti-cancer therapy, whichever occurs first. After this period, all deaths, regardless of cause, should be reported. After this period, the Sponsor should be notified if the investigator becomes aware of any serious adverse event that is believed to be related to prior study drug treatment (see Section 5.6). The investigator should follow each adverse event until the event has resolved to baseline grade or better, the event is assessed as stable by the investigator, the patient is lost to follow-up, or the patient withdraws consent. Every effort should be made to follow all serious adverse events or adverse events of special interest considered to be related to study drug or trial-related procedures until a final outcome can be reported.
- ^t In Cohort B. If a patient provides a fresh biopsy for *BRAF*^{V600} test, this sample will be used also as baseline for biomarker analysis. Therefore, predose specimens are not required for patients who provide a fresh biopsy before treatment start..
A subsequent mandatory biopsy will be performed between Days 10 and 14 of Cycle 1. An additional optional biopsy may be collected during Cycle 2, approximately 4–6 weeks after the first atezolizumab administration. A mandatory biopsy will be collected at the time of radiographic progression, if clinically feasible.
- ^u Days 10–14.
- ^v In Cohort B, atezolizumab will be given on Cycle 1, Day 15 and on Days 1 and 15 of all subsequent cycles. The initial dose will be delivered over 60 (\pm 15) minutes. If the first infusion is well tolerated all subsequent infusions will be delivered over 30 (\pm 10) minutes until a loss of clinical benefit. Study drug administration may be \pm 3 days from the scheduled Day 1 and 15 of each cycle.
- ^w Cobimetinib 60 mg/day by mouth will be given in a 21/7 dosing schedule. Dosing will start on Cycle 1, Day 1, 14 days before the first atezolizumab administration.

Appendix 1
Schedule of Activities (cont.)
Cohort C: Atezolizumab Monotherapy (21-Day Cycle)

Day (window)	Screening ^a	Cycle 1	Cycle 2	Cycle 3+	Treatment Discontinuation ^b	Unplanned Visit ^c	Survival FU ^d
	-35 to -1	1	1	1	30 (± 3) d after last dose		Q3M
Informed consent ^e	x						
Demographic data	x						
Medical history	x						
Vital signs ^{f, g}	x	x	x	x	x	x	
ECOG PS	x	x	x	x		x	
Weight	x	x	x	x	x		
Height	x						
Complete physical examination	x				x		
Limited physical examination		x ^h	x	x			
Hematology ⁱ	x	x	x	x	x	x	
Coagulation (INR and aPTT)	x						
BRAF ^{V600} WT mutation status	x						
PK/ADA sample for atezolizumab	See Appendix 2						
Serum samples for auto antibody tests ^j		x					
Optional WGS		x					

